#### **7.6.1.5 Adverse events by dose immediately before onset**

The number and incidence rate to total exposure period of adverse events and adverse drug reactions in overall and individual events classified by SOC and PT should be calculated by dose immediately before onset\*. The total exposure period is defined as the total number of days (days) each dose has been administered during the study period.

\* The tabulation unit by dose immediately before onset is as follows:

MT-6548 group: Daily dose (tabulation unit: 0 mg, 150 mg, 300 mg, 450 mg, 600 mg)

#### **7.6.1.6 Adverse events by cumulative dosage**

The number of subjects and incidence rate should be calculated for adverse events and adverse drug reactions by cumulative dosage before onset of AE for the overall events and for individual events classified by SOC and PT. The cumulative dosage will be divided into 4 categories at quartiles (0 to 1/4 of the maximum cumulative dosage, 1/4 to 2/4 of the maximum cumulative dosage, 2/4 to 3/4 of the maximum cumulative dosage, and  $\geq 3/4$  of the maximum cumulative dosage). In addition, the average number of exposure days per person should be calculated for each category. (Average number of exposure days: In the case of "0 to x/4 of the maximum cumulative dosage", the number of days until the subject concerned reaches x/4 of the maximum cumulative dosage should be calculated for each subject. In the case of  $\geq 3/4$  of the maximum cumulative dosage, the number of days to final administration for each subject and the mean should be calculated.)

#### **7.6.1.7 Adverse events before and after drug interruption**

The number of subjects and incidence rate should be calculated for adverse event and adverse drug reaction by before and after drug interruption for the overall and for individual events classified by SOC and PT. It is classified to 2 categories: 4 weeks before drug interruption and 4 weeks after drug

interruption (4 weeks after the start of drug interruption). If a subject had multiple drug interruptions and the adverse event occurred within 4 weeks after the drug interruption and within 4 weeks before the drug interruption, the subject should be counted as 1 subject for both periods.

Drug interruption period is defined as the “Planned start date of the modified dose” when “Yes” was selected in the question of “Did you choose the dosage according to the dosage adjustment algorithm?” and “Changed dose” = 0 mg in the question of “Whether the dose was changed” in the “Administration status of MT-6548” of the case report form. If “No” is selected in the question of “Did you choose dosage according to dosage adjustment algorithm?”, the subject should not be included in the calculation.

#### **7.6.2 Laboratory test values**

Descriptive statistics (except 2-sided 95% CI of the mean) should be calculated by treatment group in each evaluation time point for hematology tests, blood biochemistry tests, C-reactive protein, and VEGF. Changes from the first day of the treatment period at each evaluation time point should also be summarized.

#### **7.6.3 Resting standard 12-lead ECG**

The frequency of each decision result (normal, clinically nonsignificant abnormal, or clinically significant abnormal) should be calculated at the evaluation time point, and a shift table composed of the decision results on the first day of the treatment period and each evaluation period should be provided.

#### **7.6.4 Kt/V, Body weight after dialysis and dry weight**

Descriptive statistics (except 2-sided 95% CIs of the mean) should be calculated by evaluation time point. Changes in post-dialysis body weight and dry weight from the first day of the treatment period to each evaluation time point should also be summarized.

#### **7.6.5 Vital signs**

Descriptive statistics (except for 2-sided 95% CIs of the mean) should be calculated by evaluation time point for the items of blood pressure and pulse rate. Changes from the first day of the treatment period to each evaluation time point should also be summarized.

#### **7.6.6 Fundoscopy**

The frequency of each decision result (normal, clinically nonsignificant abnormal, or clinically significant abnormal [presence or absence of retinal hemorrhage, presence or absence of retinal edema]) should be calculated at each evaluation time point, and a shift table composed of the decision

results (normal, clinically nonsignificant abnormal, or clinically significant abnormal) should be provided on the first day of the treatment period and each evaluation time point.

#### **7.6.7 Chest X-ray**

The frequency of each decision result (normal, clinically nonsignificant abnormal, or clinically significant abnormal) should be calculated at each evaluation time point, and a shift table composed of the decision results on the first day of the treatment period and each evaluation period should be provided.

#### **7.6.8 Proportion of subjects with documented Hb values of $\geq 12.0$ g/dL or $\geq 13.0$ g/dL**

The number and proportion of subjects with confirmed Hb values  $\geq 12.0$  g/dL or  $\geq 13.0$  g/dL, after the first day of the treatment period, in each period between scheduled study visits and during the entire treatment period from the first day to Week 24 of the treatment period should be provided. If Hb value is  $> 12.0$  g/dL or  $13.0$  g/dL in the same subject, the subject should be counted as 1 in both categories.

#### **7.6.9 Proportion of subjects with documented Hb values of $< 9.0$ g/dL or $< 8.0$ g/dL.**

Subjects with confirmed Hb  $< 9.0$  g/dL or  $< 8.0$  g/dL should be analyzed in the same manner as in Section 7.6.8.

#### **7.6.10 Proportion of subjects with a documented Hb value increase rate $> 0.5$ g/dL/week**

The number and proportion of subjects in whom the Hb value increase rate is confirmed to be  $> 0.5$  g/dL/week, after the first day of the treatment period, in each period between scheduled study visits and during the entire treatment period from the first day to Week 24 of the treatment period should be provided. The Hb value increase rate in this tabulation should be calculated based on the difference in Hb values between the 2 time points measured on the scheduled study visit day in every 4 weeks (first day of the treatment period, Week 4, Week 8, Week 12, Week 16, Week 20, and Week 24 of the treatment period) and the Hb value measurement interval obtained from the actual study visit date.

#### **7.6.11 Summary statistics of Hb values before and after dose reduction or drug interruption**

Descriptive statistics of Hb values at dose reduction/interruption and after dose reduction/interruption of the study drug should be calculated. In addition, the change in Hb value after dose reduction/interruption of the study drug should be determined, and descriptive statistics should be calculated.

For the Hb value after dose reduction/drug interruption of the study drug, the data of the day closest to 4 weeks (28 days) after the Hb measurement day at dose reduction/drug interruption should be adopted. If no study drug data at the time of dose reduction/drug interruption are available, subjects

should be excluded from the Hb value analysis. In addition, the interval (days) from the Hb measurement in dose reduction/interruption of the study drug to the Hb measurement after dose reduction/interruption should be calculated, and the descriptive statistics should be provided.

### 7.6.12 Subgroup analyses

In the safety analysis set, the number and incidence ratio of subjects with adverse events and/or adverse drug reactions should be calculated for each subgroup based on the stratification factors for each endpoint in the table below.

Table 7.6.10.1 Intrinsic subgroup analysis of safety

Endpoints	Stratification factor	Stratified category
Adverse events and adverse drug reactions	Sex	Male, Female
	Age at time of consent (years)	<65, ≥65 <75, ≥75
	Dry weight (kg) on the first day of the treatment period	<60, ≥60
	Hb value (g/dL) on the first day of the treatment period	<9, 9 to <10, ≥10
	Liver function value	AST or ALT ≤ upper limit of normal, either > upper limit of normal and both ≤ 2 times the upper limit of normal, either > 2 times the upper limit of normal

Table 8.6.12.2 Extrinsic subgroup analysis of safety

Endpoints	Stratification factor	Stratified category
Adverse events and adverse drug reactions	Dose timing	Before meal, after meal, other

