3.3 Exclusion criteria

Patients who meet any of the following exclusion criteria will be excluded. Laboratory tests related to the exclusion criteria will be assessed based on central laboratory measurements. If a given laboratory test is performed multiple times during the screening period, the most recent test will be used for assessment. If blood is drawn on the day of dialysis, data before dialysis will be used for assessment.

- (1) Patients with anaemia resulting primarily from a disease other than CKD after date of consent (e.g., sickle-cell syndrome, myelodysplastic syndrome, myelofibrosis, haematopoietic malignancy, myeloma, haemolytic anaemia, thalassemia, or aplasia pure red cell)
- (2) Patients with active haemorrhaging or exsanguination within 8 weeks prior to the first day of the screening period
- (3) Patients who have received RBC transfusion within 8 weeks prior to the first day of the screening period
- (4) Patients who have received testosterone enanthate or mepitiostane within 8 weeks prior to the first day of the screening period
- (5) Patients determined by investigators/subinvestigators to likely require immediate rescue therapy or drug holiday of the study drug after initiation of treatment period

- (6) Patients who are expected to no longer require hemodialysis or hemodiafiltration due to recovery of renal function
- (7) Patients with AST, ALT, or total bilirubin values of 2.5 times or greater the upper limit of standard during the screening period. This does not apply to patients with Gilbert's syndrome.
- (8) Patients with poorly controlled hypertension (defined as a systolic blood pressure (BP) of >180 mmHg or diastolic BP of >110 mmHg) on the first day of the screening period and on the first day of the treatment period
- (9) Patients for whom any of the following apply upon funduscopy during the screening period:
 - ✓ No ocular fundus findings are possible.
 - ✓ Active ocular fundus disease
- (10) Patients with severe cardiac failure from the day of consent (Class IV according according to severity classification of the New York Heart Association [NYHA])
- (11) Patients with cerebrovascular disorders or acute coronary syndromes (hospitalization for unstable angina or myocardial infarction, etc.) within 12 weeks prior to the first day of the screening period. Patients who have been hospitalized due to acute coronary angioplasty or cardiac failure.

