## 7.3 Demographic and other baseline characteristics

For each analysis set, key demographic and other baseline characteristics are summarized. Frequency and proportion will be provided for discrete variables and descriptive statistics for continuous variables (no calculation of 95% CI of the mean). If the safety analysis set is the same as the FAS, the results for the former will not be presented.

Table 7.3 Demographic and other baseline characteristics

Category	Item	Type of variables
Subject background	Sex (male, female)	Dichotomous
	Age (years) as of informed consent	Continuous
	2 Categories: <65, ≥65	Dichotomous
	2 Categories: <75, ≥75	Dichotomous
	Duration of nephrogenic anemia (years)	Continuous
	3 Categories: <1, 1 to <5, ≥5	Ordinal
	Height (cm)	Continuous
	Dry weight (kg)	Continuous
	BMI (kg/m  )	Continuous
	2 Categories: <25, ≥25	Dichotomous
	Race	Polytomous
	3 Categories: not Hispanic nor Latino, Hispanic or Latino, Unknown	
	Ethnicity	Polytomous
3 Categories: Asian (Japanese), Asian (Other), Other		

Evaluation data	Hb value (g/dL) on the first day of the treatment period	Continuous
	3 Categories: <9, 9 to <10, ≥10	Trichotomous
	Liver function test (U/L) on the first day of the treatment period	
	3 Categories: AST and ALT both not more than upper limit of normal, either above the upper limit of normal and both ≤2 times the upper limit of normal, either >2 times the upper limit of normal	Trichotomous
	CRP (mg/dL) on the first day of the treatment period	Continuous
	Ferritin (ng/mL) on the first day of the treatment period	Continuous
	2 Categories: <100, ≥100	Dichotomous
	TSAT (%) on the first day of the treatment period	Continuous
2 Categories: <20, ≥20	Dichotomous	
Smoking status	Presence or absence of smoking status 3 Categories: never smoked, ex-smoker, current smoker	Polytomous
Underlying cause of CKD	Underlying cause 8 Categories: diabetes mellitus, hypertension, autoimmune/glomerulonephritis/vasculitis, interstitial nephritis/pyelonephritis, cystic/hereditary/congenital disease, neoplasm/tumor, unknown, other	Polytomous
Complication	Presence or absence of complications on the first day of the treatment period	Dichotomous
	Presence or absence of hypertension	Dichotomous
	Presence or absence of diabetes mellitus	Dichotomous
	Presence or absence of dyslipidemia	Dichotomous
Iron supplement	With or without iron supplements on the first day of the treatment period	Dichotomous
	2 Categories: oral, intravenous	Dichotomous

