### 7.5.6 Subgroup analyses

The following analyses should be conducted for subpopulations based on the stratification factor for each endpoint in the table below in the FAS.

(1) Hb value at Week 24 of the treatment period

LSMean, standard error, and 2-sided 95% CI should be calculated using the MMRM model (with compound symmetry [CS] for a variance-covariance matrix within subjects).

(2) Study drug mean dose at Week 20 to Week 24 of the treatment period

Descriptive statistics should be calculated.

(3) Responder rates at Week 24 of the treatment period

With respect to the responder rate at Week 24 of the treatment period (proportion of subjects with increased Hb value by  $\geq 1.0$  g/dL from the first day of the treatment period), the number of responders, proportion, and 95% CI (Clopper-Pearson [Exact] method) of the proportion should be provided.

(4) Target Hb achievement rate at Week 24 of the treatment period

The number, proportion, and 95% CI (Clopper-Pearson [Exact]) method) of the proportion of subjects with Hb levels within the target range (10.0 g/dL to  $<12.0$  g/dL) should be provided.

Table 7.5.4 Subgroup analysis of efficacy

Endpoints	Stratification factor	Stratified category
1. Hb value at Week 24 of the treatment period 2. Study drug mean dose at Week 20 to Week 24 of the treatment period 3. Responder rates at Week 24 of the treatment period 4. Target Hb achievement rate at Week 24 of the treatment period	Sex	Male, Female
	Age at time of consent (years)	<65, ≥65 <75, ≥75
	Dry weight (kg) on the first day of the treatment period	<60, ≥60
	BMI (kg/m  ) on the first day of the treatment period	<25, ≥25
	Underlying cause of CKD	Diabetes, hypertension, autoimmune/glomerulonephritis/vasculitis, interstitial nephritis/pyelonephritis, cystic/hereditary/congenital disease, neoplasm/tumor
	Duration of nephrogenic anemia (years)	<1, 1 to <5, ≥5
	Complication	Presence or absence of hypertension, diabetes, dyslipidemia
	Hb value (g/dL) on the first day of the treatment period	<9, 9 to <10, ≥10
	Liver function test (U/L) on the first day of the treatment period	AST and ALT both not more than the upper limit of normal, either above the upper limit of normal and both ≤ 2 times the upper limit of normal, either > 2 times the upper limit of normal
	CRP (mg/dL) on the first day of the treatment period	<0.31, ≥0.31

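### The first liver stratum in the safety subgroup table is worded with 'or' where two other SAP tables require both enzymes normal, so read literally the strata overlap

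*SAP*

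**What the plan says.** SAP section 7.6.12 plans the number and incidence ratio of subjects with adverse events and adverse drug reactions. These "should be calculated for each subgroup based on the stratification factors for each endpoint in the table below". Table 7.6.10.1, in that section, lists liver function beside sex, age, dry weight and baseline Hb. Its first liver category is "AST or ALT ≤ upper limit of normal". The second requires at least one enzyme to exceed the limit while neither exceeds twice the limit, and the third requires at least one to exceed twice the limit. The row is labelled only as the liver function value, with no measurement day.

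The same factor appears twice more in the SAP, with the second and third categories defined in the same way but a different first category:

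- Table 7.3 (baseline characteristics) has "AST and ALT both not more than upper limit of normal" as its first category. The variable is typed as trichotomous and tied to the first day of the treatment period.
- Table 7.5.4 (efficacy subgroups, section 7.5.6) has "AST and ALT both not more than the upper limit of normal" as its first category, again on the first day of the treatment period.

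The errata to SAP Version 2 correct several slips, including the CYP2B6 row of Table 7.5.4, but do not touch this row. Their corrected output list includes Table 14.3.11.1, the endogenous subgroup table of adverse events and adverse drug reactions, so the analysis is due to be produced.

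**The concern.** Stratum membership sets both the numerator and the denominator of each incidence ratio. With 'or', the first stratum is no longer the complement of the other two. A subject with normal AST and ALT at 1.5 times the limit meets the first and second definitions. A subject with normal AST and ALT at 2.2 times the limit meets the first and third.

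No rule says which stratum takes precedence, and nothing suggests that the overlap is intended. Where the SAP wants a subject counted in more than one category it says so, as for dose adjustments (section 7.5.2, item 5) and for the Hb thresholds of 12.0 and 13.0 g/dL (section 7.6.8). At stake is whether the row labelled normal contains only subjects with normal enzymes, and whether its size can be reconciled with the baseline table.

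**Working it through.** The plan gives no figure to reproduce here. The check has three steps.

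**1. Membership.** Put each enzyme at one of three levels: N (at or below the limit), M (above the limit, up to 2 times), H (above 2 times). This gives 9 combinations.

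| AST | ALT | Strata under 'or' (Table 7.6.10.1) | Stratum under 'both' (Tables 7.3, 7.5.4) |
|---|---|---|---|
| N | N | 1 | 1 |
| N | M | 1 and 2 | 2 |
| N | H | 1 and 3 | 3 |
| M | N | 1 and 2 | 2 |
| M | M | 2 | 2 |
| M | H | 3 | 3 |
| H | N | 1 and 3 | 3 |
| H | M | 3 | 3 |
| H | H | 3 | 3 |

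Under 'or', 4 of 9 combinations fall in two strata. Under 'both', each falls in exactly one (1 in stratum 1, 3 in stratum 2, 5 in stratum 3), with no gap. Strata 2 and 3 hold the same combinations in both columns. Only stratum 1 changes, and it gains exactly the subjects with one normal and one raised enzyme.

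**2. Whether such subjects can be enrolled.** Protocol section 3.3, criterion 7, excludes "Patients with AST, ALT, or total bilirubin values of 2.5 times or greater the upper limit of standard during the screening period" (with an exception for Gilbert's syndrome). Values below 2.5 times the limit are admitted, so all three strata can be populated.

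**3. Size.** Inputs: 20 subjects (Protocol section 6.1; SAP section 2.3), all assumed to be in the safety analysis set; k subjects with exactly one raised enzyme, assumed 0 to 3 because the documents give no enzyme distribution; none with both raised (assumed). Let e be the number with an event among the 20 − k subjects with both enzymes normal, and f the number with an event among the k.

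- Proportion in stratum 1 under 'both': e/(20 − k)
- Proportion in stratum 1 under 'or': (e + f)/20
- Shift: (e + f)/20 − e/(20 − k) = (k/20) × [f/k − e/(20 − k)]

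The bracket lies between −1 and 1, so the shift is at most k/20 in either direction:

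- k = 0: 0
- k = 1: 1/20 = 5 percentage points
- k = 2: 2/20 = 10 percentage points
- k = 3: 3/20 = 15 percentage points

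The bound for k = 3 is reached at e = 0, f = 3 (0/17 becomes 3/20) and at e = 17, f = 0 (17/17 becomes 17/20). If m subjects had both enzymes raised, the bound would be k/(20 − m).

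**The case against.** The strongest reply is that the intent is plain. The second and third categories in the same cell leave both enzymes normal as the only remainder, the SAP defines the factor that way twice elsewhere, and the document is a translation from Japanese. A programmer would probably code the factor once and use it everywhere, so double counting is not certain. That stands: the supportable claim is an inconsistent definition that overlaps if followed literally. It does not remove the need to correct the text, because the safety table is the one that governs this output and the errata passed over it.

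Two stronger readings are tempting and should not be drawn.

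- A reader might infer that this weakens the trial's check for a hepatic signal. The SAP does not give the table that role. It tabulates all adverse events by a patient characteristic. Liver laboratory values and their changes are summarised under section 7.6.2, and individual events under section 7.6.1.2; neither uses these strata.
- A reader might infer that a contrast between liver groups is diluted. Section 7.6.12 plans counts and incidence ratios only, with no test, interval or between-stratum comparison. With 20 subjects across three strata, such a comparison would tell little under either wording.

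It is also fair to say that the lower end of the assumed range is no effect, and that overlap between the first and third strata is likely to be uncommon given the screening limit of 2.5 times, although first-day values may differ from screening values.

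**Conclusion.** The point holds as a minor inconsistency in a stated analysis rule. As written, Table 7.6.10.1 conflicts with Tables 7.3 and 7.5.4, and its strata are not mutually exclusive: subjects with exactly one raised enzyme enter the normal stratum as well as their proper one. Only the normal stratum's denominator and adverse event proportion are contaminated. The shift is 0 to at most 15 percentage points, on the assumptions of 0 to 3 such subjects among 20 and none with both enzymes raised. The consequence is confined to one row of a descriptive safety subgroup table, and no primary or other efficacy result depends on it. The missing measurement day is a second, smaller gap in the same row: even with the conjunction corrected, agreement with the baseline table is not assured until the day is stated.

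**What to change.** In SAP Table 7.6.10.1, replace the first liver category with the condition used in Table 7.5.4, "AST and ALT both not more than the upper limit of normal", and leave the second and third categories as they are. Label the row as measured on the first day of the treatment period, as Tables 7.3 and 7.5.4 do. The strata are then mutually exclusive and exhaustive for subjects with both enzymes measured, and can be derived once for all three tables. The cost is one phrase and one row label, made as a further erratum; no new data or analysis is needed.

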## 8. Software to Use

SAS for Windows (Release 9.4) will be used for statistical analysis.

## 9. Changes in the Statistical Analysis Plan from the Study Protocol

- (1) Mean corpuscular volume and mean corpuscular hemoglobin were added to the other efficacy endpoints.

Reason: Because the importance of mean corpuscular volume and mean corpuscular hemoglobin has increased in the efficacy evaluation from a clinical point of view.

